2.2 Hypotheses and/or Estimations

The primary clinical hypothesis of Study 20170703 is that preventive treatment with monthly injections of erenumab is superior to placebo in achieving MOH remission for subjects with CM-MOH in the nonopioid-treated cohort who have a history of at least 1 preventive treatment failure as measured by the absence of the MOH status based on the mean over months 4, 5, and 6 (**week 13 through 24**) of the DBTP.

The secondary clinical hypotheses of Study 20170703 are that preventive treatment with monthly injections of erenumab is superior to placebo in reducing AHMDs over months 4 to 6 (**week 13 through 24**) of the DBTP; sustaining MOH remission during the entire DBTP; reducing migraine-related impact on physical functioning and everyday activities as measured by Migraine Physical Function Impact Diary (MPFID) physical function and everyday activities domains (non-EU) or migraine-related impact on physical functioning as measured by the Headache Impact Test 6 (HIT-6) (EU only).

For subjects with CM-MOH allocated to the opioid-treated cohort, an additional exploratory clinical hypothesis of Study 20170703 is that preventive treatment with monthly injections of erenumab could help reduce opioid use as measured by the mean change in monthly opioid medication days from baseline over months 4, 5, and 6 (**week 13 through 24**) of the DBTP. Formal statistical testing does not apply to this exploratory clinical hypothesis.

3. Study Overview

3.1 Study Design

Study 20170703 is a phase 4, randomized, double-blind, double-dummy, parallel-group, placebo-controlled study to evaluate the safety and efficacy of erenumab against placebo in a CM population with MOH and prior history of treatment failure. Subjects will be enrolled based on fulfillment of the International Classification of Headache Disorders, 3rd Edition (ICHD-3) CM and MOH criteria and will not be advised to early discontinue acute medication. During randomization, subjects will be separated into 2 distinct cohorts based on their opioid medication use at baseline. Subjects with an opioid medication use > 4 days per month during the baseline period will be allocated to the opioid-treated cohort. Subjects with an opioid medication use of ≤ 4 days per month during the baseline period will be allocated to the nonopioid-treated cohort. The randomization process on the nonopioid-treated cohort will be balanced based on the following stratum:

- Concomitant oral migraine preventive treatment initiated before screening and taken during baseline (Yes or No).

Subjects allocated to the opioid treated cohort will be analyzed separately as an exploratory cohort.

During the DBTP, subjects will be randomized in a 1:1:1 fashion to either placebo, erenumab 70 mg SC every 4 weeks, or erenumab 140 mg SC every 4 weeks. Subjects who successfully complete the 24-week DBTP of the study will be offered an opportunity to continue in an OLTP of 28-weeks duration. Subjects who received erenumab treatment during the DBTP will continue to receive the same erenumab dose during the OLTP. Subjects who received placebo during the DBTP will be allocated in a 1:1 ratio to receive either erenumab 70 mg or 140 mg SC QM during the OLTP. All subjects will remain blinded to their original DBTP treatment assignment.

3.2 Sample Size

The sample size calculation has been performed based on the primary endpoint (absence of MOH at month 6) for the nonopioid-treated cohort.

Based on a subgroup analysis of subjects who failed preventive migraine medication, overused acute headache medication, and had at least 14 MHD at baseline in the erenumab CM pivotal Study 20120295, 33.1%, 50.5%, and 64.1% of subjects in placebo, erenumab 70 mg and erenumab 140 mg treatment group, respectively,

achieved absence of MOH at month 3. Assuming similar response rates over month 4, 5 and 6 and a conservative scenario that includes a dropout rate of 20% during the 6-month DBTP, the planned sample size of 183 subjects per group will provide 85% power for 70 mg versus placebo and > 99% power for 140 mg versus placebo using a 2-sample chi-squared test with a 2-sided significance level of 0.05.

In addition, up to 138 opioid-treated cohort subjects will be randomized to receive erenumab or placebo (46 on placebo, 46 on 70 mg, and 46 on 140 mg).

3.3 Adaptive Design

Not applicable.

4. Covariates and Subgroups

4.1 Planned Covariates

All model-adjusted analyses of efficacy endpoints in nonopioid-treated cohort will include the following covariates:

- Concomitant oral migraine preventive treatment initiated before screening AND taken during baseline (Yes or No)
- Corresponding baseline value for the endpoint being analyzed (for continuous endpoints only)

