Mean monthly AHMD < 10 days OR mean MHD < 14 days over 3 consecutive study months, **excluding gepant-based medication in the derivation.**

Sustained MOH Remission (Over 6 Months During DBTP)

Mean monthly AHMD < 10 days OR mean MHD < 14 days over 3 consecutive study months **at both time points** (months 1, 2, and 3 [week 1 to week 12], AND months 4, 5, and 6 [week 13 through 24]), **excluding gepant-based medication in the derivation.**

Absence of MOH at End of Study

Mean monthly AHMD < 10 days OR mean MHD < 14 days over months 11, 12 and 13 (week 41 through 52), **excluding gepant-based medication in the derivation.**

Sustained Absence of MOH (Sustained MOH Remission) Over 1 Year

Absence of MOH over the DBTP (months 1, 2, and 3 [week 1 through 12], OR months 4, 5, and 6 [week 13 through 24]) AND OLTP (months 11,12 and 13 [week 41 through 52]), **excluding gepant-based medication in the derivation.**

Conversion to Episodic Migraine (EM) (Over 3 Months)

Mean MHD < 14 days over 3 consecutive study months

Achievement of Conversion to Episodic Migraine (EM) (Over 6 Months During DBTP)

Mean MHD <14 days over months 1 through 6 (week 1 through 24) of the DBTP.

Qualified Headache

A qualified headache is defined as

- A headache of duration ≥ 4 hours, or
- A headache of duration < 4 hours during which an acute headache medication is administered

Headache Day

A calendar day (00:00 to 23:59) in which the subject experiences ≥ 1 qualified headache or takes ≥ 1 acute migraine-specific medication (ie, triptan, ergotamine, **ditan**) during aura

Qualified Migraine Headache

A qualified migraine headache is defined as

- A headache lasting for ≥ 4 hours, and meeting ≥ 1 of the following criteria (a and/or b):
 - a) ≥ 2 of the following pain features:
 - Unilateral
 - Throbbing
 - Moderate to severe (ie, headache pain intensity ≥ 4)
 - Exacerbated with exercise/physical activity
 - b) ≥ 1 of the following associated symptoms:
 - Nausea
 - Vomiting
 - Photophobia and phonophobia
- A headache during which an acute migraine-specific medication (ie, triptan, ergotamine, **ditan**) is administered regardless of the headache duration, pain features, and associated symptoms

Migraine Day

A calendar day (00:00 to 23:59) in which the subject experiences ≥ 1 qualified migraine headache or takes ≥ 1 acute migraine-specific medication (ie, triptan, ergotamine, **ditan**) during aura.

Migraine-free Day

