8.3.1 Missing Baseline Evaluation

Missing baseline evaluations will not be imputed.

All subjects included in the efficacy analysis set will have baseline monthly rate or monthly average of migraine and non-migraine headaches related measurements after applying proration rule defined in [Section 5.1.1](#) since only subject with $\geq 80\%$ compliance of eDiary use during baseline will be eligible for randomization.

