8.3.2 Missing Post-baseline Evaluation in Double-blind Treatment Period

Primary analysis of dichotomous efficacy endpoints during the DBTP will be conducted using Cochran-Mantel-Haenszel test (CMH) after the missing data are imputed as nonresponse. Primary analysis of continuous efficacy endpoints during the DBTP will be conducted using the repeated measures linear mixed effects model including observed data without imputation.

For the descriptive summary of mean monthly value calculated using the monthly value from each of months 4, 5, and 6 (**week 13 through 24**) of the DBTP, if a subject has at least one monthly value at months 4, 5, and 6 (**week 13 through 24**), then the subject contributes to the summary statistics.

If the proportion of missing data in primary endpoint is high (eg, > 20% for primary analysis at week 24), further analysis will be performed to

- examine the frequency and reason of missing data
- determine if there are any patterns in the missing data
- distinguish true missing values from other unknown values (eg, due to measurement or sample processing error)

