9.4 Demographic and Baseline Characteristics

Subject demographic and baseline characteristics will be summarized using descriptive statistics by randomized treatment group and overall study population using FAS. If multiple races have been reported for a subject, the subject will be categorized as multiple races.

At double-blinded baseline, following demographic and baseline characteristics will be summarized:

- Age (years)
- Sex
- Ethnicity
- Race
- Region (North America vs Others)
- Height (cm)
- Weight (kg)
- Body mass index (BMI, kg/m²)
- Targeted neurological disease diagnosis at baseline
- **Prior history of treatment with onabotulinumtoxinA**
- **Prior history of depression**
- Disease duration of migraine with or without aura
- **Disease duration of chronic migraine with or without aura**
- Age at onset of migraine
- Age at onset of chronic migraine
- **Prior migraine preventive treatment and reasons for discontinuation by medication category**
- **Concomitant oral migraine preventive treatment by medication category**
- **Number of prior migraine preventive treatment failures by medication category**
- Acute headache medication used during baseline period:
 - a) Migraine-specific
 - b) Non-migraine-specific
- Monthly migraine days during baseline period
- **Monthly migraine-free days during baseline period**
- Monthly headache days during baseline period

- Monthly **headache** days with **at least** moderate pain intensity during baseline period
- Monthly acute migraine-specific medication days during baseline period
- Monthly acute migraine-specific medication days during baseline period among baseline users
- Monthly acute headache medication days during baseline period
- **Monthly opioid/opioid-containing medication days (opioid-treated cohort only)**
- **Overuse of acute headache medication during the baseline period**
- Overuse of triptan during the baseline period
- Overuse of simple analgesics/NSAIDs during the baseline period
- Overuse of combination analgesics during the baseline period
- Overuse of combination therapies during the baseline period
- Monthly average **headache** pain intensity during baseline period
- **Monthly average MPFID physical impairment score during baseline period**
- **Monthly average MPFID overall impact on everyday activities score during baseline period**
- Beck Depression Inventory (BDI)-II total score severity grade
- Headache Impact Test (HIT-6) total score
- MFIQ impact on physical functioning

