9.5 Efficacy Analyses

The primary analysis of efficacy endpoints **during the DBTP** will utilize the efficacy analysis set. Subjects will be analyzed according to their randomized treatment group regardless of the actual treatment received during the study.

Table 9-1. Primary Efficacy Endpoint Summary Table

Endpoint	Primary Summary and Analysis Method	Sensitivity Analysis
Absence of MOH at month 6 (week 24) as defined by mean monthly AHMD < 10 days over months 4, 5, and 6 (week 13 through 24) OR mean MHD < 14 days over months 4, 5 and 6 (week 13 through 24) where AHMD include any eDiary day in which an acute headache medication intake is reported.	
 The responder rate of subjects with absence of MOH by treatment group with missing data imputed as non-response imputation (NRI) A stratified CMH test with NRI adjusted by original stratified values Breslow-Day test will be conducted to test the homogeneity of the odds ratios across the original stratification factors 	
 Same as primary analysis method but using observed concomitant oral preventive medication status as the stratification factor. Same as primary analysis method but only include subjects with observed monthly AHMD and MHD in each of the month over month 4, 5 and 6

Table 9-2. Secondary Efficacy Endpoints Summary Table

Endpoint	Primary Summary and Analysis Method	Sensitivity Analysis

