
 Change from baseline in mean monthly AHMD over months 4, 5, and 6 (week 13 through 24) of the DBTP (Note: Result at each timepoint during DBTP will also be generated in the same model.) 	
 Summary statistics by visit using observed data and 95% CI of mean change from baseline at each visit by treatment group Least squares means by visit using a linear mixed effects repeated measure model adjusted by baseline value, original stratification factor, scheduled visit, and the interaction of treatment group with scheduled visit, without any imputation for missing data at monthly level Treatment difference between each erenumab dose group and placebo) with the 95% CI, and p-value from the model in #2 	Least squares means by visit using a linear mixed effects repeated measure model adjusted by baseline value, observed concomitant oral migraine preventive medication status, scheduled visit, and the interaction of treatment group with scheduled visit, without any imputation for missing data at monthly level

Endpoint	Primary Summary and Analysis Method	Sensitivity Analysis
2. Sustained MOH remission during DBTP, as defined by absence of MOH at months 3 (week 12) and 6 (week 24) of the DBTP, and “absence of MOH” is achieved when mean monthly AHMD < 10 days OR mean MHD < 14 days over the respective 3-month period	Same as primary endpoint	Same as primary analysis method but using observed concomitant oral preventive medication status as stratification factor.
3. Change from baseline in mean monthly average physical impairment domain scores as measured by the MPFID over months 4, 5, and 6 (week 13 through 24) of the DBTP (non-EU region) 4. Change from baseline in mean monthly average impact on everyday activities domain scores as measured by the MPFID over months 4, 5, and 6 (week 13 through 24) of the DBTP (non-EU region) 5. Change from baseline in mean HIT-6 total score over months 4, 5, and 6 (week 13 through 24) of the DBTP (EU region) (Note: Result at each timepoint during DBTP will also be generated in the same model.)	Same as above	Same as above

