9.5.1 Analyses of Primary Efficacy Endpoint

The primary comparison of absence of MOH at month 6 between each erenumab group and placebo will be analyzed using a stratified CMH test with nonresponse imputation. The proportion of subjects with absence of MOH will be reported for each treatment group. The odds ratio between each erenumab group and placebo, the corresponding 95% CI and p-value will be reported. **Breslow-Day test will be conducted to test the homogeneity of the odds ratios across the strata.**

As a supportive analysis, the primary efficacy endpoint will also be analyzed including subjects with observed AHMD and MHD data at each month during months 4, 5, and 6 (week 13 through 24).

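### The CMH test of absence of MOH is valid but leaves out baseline MHD and AHMD, the two counts that define the endpoint; adjusting for them would add about 0 to 5 points of power at the 70 mg primary test with no new data

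*SAP*

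**What the plan says.** SAP 5.1.1 defines absence of MOH as "Mean monthly AHMD < 10 days OR mean MHD < 14 days over 3 consecutive study months". For dichotomous endpoints SAP 8.3.2 states: "Primary analysis of dichotomous efficacy endpoints during the DBTP will be conducted using Cochran-Mantel-Haenszel test (CMH) after the missing data are imputed as nonresponse". SAP Table 9-1 gives the primary method as "A stratified CMH test with NRI adjusted by original stratified values", and SAP 9.5.1 adds: "Breslow-Day test will be conducted to test the homogeneity of the odds ratios across the strata". The only stratum is concomitant oral preventive use. SAP 4.1 limits the baseline covariate in these terms: "Corresponding baseline value for the endpoint being analyzed (for continuous endpoints only". Neither primary sensitivity analysis in Table 9-1 (observed stratum; subjects observed in all three months) uses baseline counts.

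The baseline counts are available. SAP 8.3.1 states: "All subjects included in the efficacy analysis set will have baseline monthly rate or monthly average of migraine and non-migraine headaches related measurements". The characteristics tabulated under SAP 9.4 include "Monthly acute headache medication days during baseline period" and the matching headache-day count. For continuous AHMD, Table 9-2 already specifies "Least squares means by visit using a linear mixed effects repeated measure model adjusted by baseline value, original stratification factor".

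Protocol 10.2.2 names the corresponding baseline value as a covariate for all formal efficacy analyses in the nonopioid cohort, without limiting it to continuous endpoints. Protocol 10.4.2.1 and 10.4.2.2 nevertheless prescribe the stratified CMH test. SAP Section 10, which lists changes from the protocol, does not mention the narrower wording in SAP 4.1.

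**The concern.** Whether a subject falls below 14 headache days or 10 medication days at months 4 to 6 plausibly depends on how far above those limits the subject started. The CMH test ignores this distance. The continuous AHMD analysis, built from the same diary, does not.

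The place where it could matter is the 70 mg primary comparison, step 4 of the fixed sequence. A miss there stops 70 mg AHMD, 70 mg sustained remission and every patient-reported endpoint for both doses. It is also the weaker of the two primary comparisons, with a stated power of 85%.

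The wording of Protocol 10.2.2 is a separate, clerical matter. Read literally, it would add baseline MOH status, which is nearly constant because Protocol 6.3 requires at least 14 headache days and medication overuse at entry. It does not already require adjustment for the two counts.

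**Working it through.** **Inputs from Protocol 10.1 and SAP 3.2:** response 33.1% (placebo), 50.5% (70 mg), 64.1% (140 mg); 183 per arm; 20% dropout; two-sided 0.05; two-sample chi-squared test.

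**Formula.** Power = Φ(z), with z = (Δ − 1.96·s0)/s1, s0 = √[2·p̄(1−p̄)/n], s1 = √{[p0(1−p0) + p1(1−p1)]/n}, where Δ = p1 − p0 and p̄ is their mean.

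**Step 1: reproduce the stated 85%.** Dropouts removed: n = 183 × 0.8 ≈ 146. Δ = 0.174, s0 = 0.0577, s1 = 0.0568, z = 1.071, power 85.8%. The stated figure reproduces.

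**Step 2: power under the planned nonresponse imputation.** All 183 per arm stay in, and both rates are multiplied by (1 − imputed share).

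| Imputed as nonresponse | Placebo | 70 mg | z | Power |
|---|---|---|---|---|
| 5% | 31.4% | 48.0% | 1.290 | 90.1% |
| 10% | 29.8% | 45.5% | 1.147 | 87.4% |
| 15% | 28.1% | 42.9% | 1.008 | 84.3% |
| 20% | 26.5% | 40.4% | 0.872 | 80.8% |

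For 140 mg at 20% imputed (26.5% vs 51.3%), z = 3.005 and power is 99.9%.

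**Step 3: gain from adjustment, by simulation.** There were 10,000 trials per setting, with a Monte Carlo standard error of the paired difference of at most 0.29 points. Assumptions, none given in the documents:
- Baseline MHD 14 to 28 (mean 20.2), AHMD 10 to 28 (mean 17.4), correlation 0.41, equal weights.
- Latent-normal response calibrated to 33.1% and 50.5%.
- Stratum prevalence 35%; dropout independent of outcome and set to nonresponse.
- R² is the share of the latent outcome explained by the two baseline counts.

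The CMH chi-squared test (no continuity correction) was compared with logistic regression standardised to a marginal odds ratio, tested by a Wald test on its log. Entries are adjusted minus CMH power, in points.

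| Imputed | R² 0 | R² 0.1 | R² 0.2 | R² 0.3 |
|---|---|---|---|---|
| 20% | −0.6 | +1.2 | +3.2 | +5.5 |
| 15% | −0.3 | +1.2 | +2.8 | +5.5 |
| 10% | +0.1 | +1.5 | +3.5 | +4.8 |
| 5% | +0.2 | +1.6 | +3.0 | +4.5 |

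Variants at 20% imputed, for R² 0.1, 0.2 and 0.3:
- Prognostic stratum (odds ratio 2 to 4): +1.3 to +1.6, +2.4 to +3.1, +4.4 to +4.7.
- 40% of subjects entering at the 15-day NSAID threshold: +1.2, +3.3, +4.7.

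**Step 4: model the counts directly.** Months 4 to 6 means of MHD and AHMD with SD 6 days and residual correlation 0.6; response if MHD < 14 or AHMD < 10. Gain by assumed correlation of each baseline count with its follow-up count:

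| Correlation | 0.2 | 0.3 | 0.4 | 0.5 | 0.6 |
|---|---|---|---|---|---|
| 20% imputed | 0.0 | +0.7 | +1.5 | +3.1 | +4.5 |
| 10% imputed | +0.5 | +1.2 | +2.1 | +3.3 | +4.7 |

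A second counts simulation (4,000 trials per setting, somewhat different baseline assumptions, stratum not prognostic) gave +0.3, +1.9, +2.1, +3.4 and +5.2 for the standardised estimate at the same correlations with 20% imputed. On 146 completers per arm it gave +0.9, +1.3, +3.2, +4.6 and +6.3.

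**Step 5: type I error and the odds ratio.** Null settings (20,000 trials each) gave 4.8 to 5.1% for the adjusted test and 4.7 to 5.2% for CMH. At 20% imputed the marginal odds ratio is (0.404/0.596)/(0.2648/0.7352) = 1.88. The Mantel-Haenszel odds ratio is 1.88, 1.90, 1.94 and 1.97 for a stratum odds ratio of 1, 2, 3 and 4, so the two agree only if the stratum is not prognostic.

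**The case against.** The plan contains no error here. Stratified CMH with nonresponse imputation is named consistently in both documents, it stratifies by the randomisation factor, and SAP 4.1 makes the limit to continuous endpoints visible. The benefit depends on a prognostic strength the documents do not state. Eligibility truncates both counts from below, which restricts their range, so a gain near zero is possible. Only step 4 has a computable benefit, and it is reached only if steps 1 to 3 succeed. The proposal changes the named test at steps 1, 3, 4 and 6, late in a SAP already amended in December 2022. Adding a baseline-count category to the CMH strata would be a smaller step.

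Most of this stands as description, and it is why the point concerns efficiency only. It does not remove the case for adjustment. The possible loss is small and the covariates are already derived. The gain is similar whether 5% or 20% are imputed, so it does not rely on the 81% starting point. That low figure would need every dropout to become a nonresponder, although Protocol 8.1 asks subjects who stop treatment to keep the diary. Extra CMH strata would use part of the same information, but that was not evaluated here and would need the same documented change.

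**Conclusion.** The concern holds as an efficiency point of moderate weight. The planned test controls type I error and is not in doubt. Adjusting for baseline MHD and AHMD would raise power for 70 mg versus placebo by about 0 to 5 points (simulated range −0.6 to +5.5 under nonresponse imputation; up to 6.3 on a completer basis at correlation 0.6). To buy the same power by enrolment at 20% imputed, the Step 1 formula needs about 8, 16 or 27 more subjects per arm for +1.5, +3 or +5 points.

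The size rests entirely on the assumed prognostic strength. At a correlation of 0.3 or less the gain is about 1 to 2 points at most. The 140 mg primary test gains nothing. The gain for sustained remission cannot be computed, because the documents give no rates for it. The mismatch in Protocol 10.2.2 is a wording matter and adds nothing to this weight.

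**What to change.** Before the nonopioid cohort is unblinded:

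1. For absence of MOH and, for consistency, sustained remission, pre-specify a logistic regression on treatment, randomisation stratum, baseline monthly MHD and baseline monthly AHMD. Keep nonresponse imputation as planned. Test and report the standardised (marginal) odds ratio with its 95% CI.
2. State in the primary and sustained-remission estimands that the odds ratio is marginal; at present they say only that it is an odds ratio.
3. Keep the stratified CMH test with its Breslow-Day check as supportive.
4. Record the change in SAP Section 10.
5. Separately, align Protocol 10.2.2 with Protocol 10.4.2 and SAP 4.1.

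Naming the adjusted model only as a sensitivity analysis would leave the confirmatory power unchanged.

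The cost is one extra model and a documented protocol and SAP change, because the test named in Protocol 10.4.2 changes at steps 1, 3, 4 and 6. No new data are needed. Power falls by at most 0.6 points if the baseline counts turn out not to be prognostic. If the stratum is prognostic, the reported odds ratio will sit slightly below the CMH value (1.88 against 1.90 to 1.97 under the planning rates).
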